Neuromodulation in Lower Limb Amputees

NCT 04543786

Last document update: Mar. 17, 2022

Background:

Limb amputation results in an extreme form of peripheral nerve injury. Damage to peripheral nerves, such as with neuropathy, crush injuries, nerve transection, or limb amputation often results in chronic pain, which may be associated with altered excitability of spinal sensorimotor pathways. These spinal pathways become hyperexcitable due to a lack of sensory input, which causes tonic disinhibition of descending circuits and spontaneous activity in the dorsal root ganglia. Spinal excitability can be measured using the H-reflex, in which electrical stimulation of muscle spindle Ia afferents activates spinal motoneurons via the myotatic reflex, as well as the posterior root-muscle (PRM) reflex, which is elicited by transcutaneous stimulation over the dorsal roots and is considered to be half of the H-reflex, excluding the peripheral primary afferents, but with multiple root activation. Spinal excitability has not been measured in amputees but may offer a potential biomarker for phantom limb pain (PLP). Neuromodulation may restore normal spinal excitability and reduce PLP, thus offering the potential to improve the quality of life in individuals with a lower limb amputation. The results of this study will provide the foundation for future development of a neuroprosthesis to restore spinal excitability and reduce PLP in individuals with a lower limb amputation.

Objectives:

The overall goal of this work is to investigate the changes in the spinal cord resulting from limb amputation. Specifically, we measured spinal cord excitability using posterior root-muscle (PRM) reflexes in people with a transtibial amputation. We hypothesized that spinal reflexes would be hyperexcitable, indicated by lower thresholds to evoke the reflexes, because of the neuropathic pain state. We applied tSCS each day for 5 days, targeting the dorsal roots corresponding to the distal limbs. We hypothesized that, after 5 days of tSCS, spinal reflex hyperexcitability and PLP would decrease.

Design:

Participants underwent 5 testing and stimulation sessions in 1 week.

We recruited individuals with a unilateral transtibial amputation and who experienced phantom limb pain. To measure spinal cord excitability, we studied PRM reflexes, which were recorded using electromyography (EMG) electrodes placed on the residual limb. We placed bipolar electromyography (EMG) electrodes on the lateral gastrocnemius (LG), medial gastrocnemius (MG), tibialis anterior (TA), and vastus lateralis (VL) muscles and a high-density EMG electrode grid across the putative gastrocnemius muscles. We positioned a ground electrode onto the patella of the residual limb. We recorded EMG data at a sampling rate of 4000 Hz and streamed the data into MATLAB. We delivered stimulation using a DS8R stimulator with a firmware update to allow frequencies up to 10 kHz.

We attempted to elicit H-reflexes by electrically stimulating the tibial nerve of the residual limb. Stimuli consisted of a 1-ms long monophasic, cathodic, square wave pulse. We varied the stimulation amplitude to determine the thresholds for the M-wave as well as the maximum amplitude of the M-wave. We elicited the PRM reflex in the residual limb by electrically stimulating the spinal dorsal roots. We placed round adhesive electrodes paravertebrally of the T12-L1 spinous processes. We placed return electrodes on each anterior superior iliac spine. We wrapped

the participant's torso using Coban wrap and placed a small piece of foam between the tSCS electrodes and the back of the chair. The stimulation pulses to evoke the PRM reflex were 1-ms long monophasic, cathodic, square wave pulse. For the purpose of evoking PRM reflexes in the residual limb, we stimulated through the tSCS electrode ipsilateral to the residual limb only. We determined the stimulation threshold for evoking a PRM reflex in the gastrocnemius muscles, followed by the maximum PRM reflex amplitude. The maximum PRM reflex amplitude was at either the stimulation amplitude past which the magnitude of the PRM reflex no longer increased or the maximum stimulation amplitude tolerated by the participant. In this study, we did not exceed a stimulation amplitude of 180 mA. We varied the stimulation amplitude to obtain recruitment curves for the M-waves PRM reflexes. Specifically, we stimulated 15 amplitudes between 5 mA below threshold and 10-15 mA above the M-wave maximum (or PRM reflex maximum) if tolerated or up to 180 mA in a random order. Each amplitude was repeated four times and stimuli were delivered 10 s apart.

We performed the pain pressure threshold test using an algometer. The pain pressure threshold test measures the minimum amount of pressure that the participant can tolerate at a specific location. We pushed the rubber tip (1 cm diameter) of the algometer onto the skin over muscle (not pushing on bone) on several locations of both the residual and intact limbs. The participant reported when the pressure became painful, at which point we removed the algometer and recorded the pressure magnitude.

We asked participants to rate their PLP in the last 24 hours using a visual analog scale (VAS) from 0 and 10, where 0 indicated no pain at all, and 10 indicated the worst pain imaginable. Participants completed the short-form McGill Pain Questionnaire to describe their pain prior to participation in the study as well as throughout the week. The McGill Pain Questionnaire evaluates the sensation, temporal changes, and strength of pain. The total McGill Pain Questionnaire score indicates the intensity and affect the pain has on their life, and a 5-point change in McGill Pain Questionnaire is considered clinically meaningful.

We delivered bilateral tSCS for neuromodulation continuously for 30 minutes, with a break at 15 minutes to inspect the stimulation site. The tSCS consisted of 1 ms long pulses with a 10 kHz carrier frequency, delivered at 30 Hz. We started with a low amplitude of stimulation (approximately 10-20 mA) and slowly increased the stimulation beyond PRM reflex threshold, according to the comfort of the participant.

All data were collected while the participant sat comfortably in a chair. At the beginning of each day, the participant rated their PLP over the last 24 hours using the VAS. We marked the location of the stimulation and EMG electrodes with a permanent marker to ensure consistent placement across the 5 days. Every day, we performed the M-wave and PRM reflex measures, followed by high-frequency tSCS for 30 minutes. At the beginning of the first and fifth days, the participant completed the McGill Pain Questionnaire, and we performed the pain pressure threshold test.

Study Protocol for study using transcutaneous spinal cord stimulation in lower limb amputees

Before participant comes in:

1. A00 = control port on stimulator
2. P00 = trigger port on stimulator
3. A01 = DIGI port on TMSi
4. TMSi cables: HDEMG, 2x BPEMG, IMU
5. PW on stimulator = 1000 us; 100%, 10 us; Monophasic, negative; 10 V = 180 mA
6. Make sure Stimulator output is **disabled**

Pain Assessments:

1. Give participant MPQ, GQPLA Day 1: Day 5:
2. Give participant VAS Day 1: Day 2: Day 3: Day 4: Day 5:
3. Use algometer to get pain threshold in the following regions:

Residual limb	Day 1 (lbf)	Day 5 (lbf)
Bottom of stump		
Anterior 5 cm above stump		
Posterior 5 cm above stump		
Medial 5 cm above stump		
Lateral 5 cm above stump		
Anterior 10 cm above stump		
Posterior 10 cm above stump		
Medial 10 cm above stump		
Lateral 10 cm above stump		
Mid-quad		
Mid-hamstring		
Intact limb		
On heel		
Ball of foot		
Top of foot		
Back of ankle		
Mid-shin (TA)		
Mid-calf		
Mid-quad		
Mid-hamstring		
Left arm		
Mid-biceps		
Right arm		
Mid-biceps		

Prep Participant:

1. Prep skin on amputated limb
2. Place and tape EMG electrodes
 - a. HDEMG: SOL; BP1: LG; BP2: MG; BP3: TA; BP4: Q
 - b. Orientation of grid: _____
3. Place IMU on lateral side of stump
4. Place tibial nerve electrodes
5. Wrap the leg in Coban
6. Place tSCS electrodes: **2** round adjacent to T12 (L1 = belly button, L4 = IC); **2** rect on ICs
7. Turn on TMSi

Record Impedances:

1. Run reflex GUI (*StimHreflexTMSiv15.m*)
2. Change name of file to "SubjectID_DayX_Impedacnes_R1", reset counter to 1
Day 1: Day 2: Day 3: Day 4: Day 5:

tSCS threshold:

3. Place foam behind participant's back
4. Make sure stimulator PW is 1000 us
5. Change name of file to "SubjectID_DayX_tSCSthresh_R1", reset counter to 1
6. Make sure GUI in PRM-reflexes mode
7. Calibrate stimulator
8. **Enable** stimulator
9. Set stimulation amplitude to 10 mA
10. Stimulate single pulses
11. Increase in 5 mA increments until have PRM-reflex in 1 of 3 stimulations
12. Note down tSCS threshold:
Day 1: occurred at _____ mA in _____ muscle
Day 2: occurred at _____ mA in _____ muscle
Day 3: occurred at _____ mA in _____ muscle
Day 4: occurred at _____ mA in _____ muscle
Day 5: occurred at _____ mA in _____ muscle

tSCS PRM max:

1. Change name of file to "SubjectID_DayX_tSCSmax_R1", reset counter to 1
2. Stimulate at 5 mA above threshold and observe PRM response
3. Increase by 5-10 mA until have maximum amplitude
4. Note down tSCS max:

Day 1: occurred at _____ mA in _____ muscle. Max defined by: _____
Day 2: occurred at _____ mA in _____ muscle. Max defined by: _____
Day 3: occurred at _____ mA in _____ muscle. Max defined by: _____
Day 4: occurred at _____ mA in _____ muscle. Max defined by: _____
Day 5: occurred at _____ mA in _____ muscle. Max defined by: _____

5. **Disable** stimulator

tSCS recruitment curve:

1. Calibrate stimulator
2. **Enable** stimulator
3. Change name of file to "SubjectID_DayX_tSCSRC_R1", reset counter to 1
4. Set limits to below threshold and above max

a. Amplitude range:

Day 1: _____ mA to _____ mA, notes: _____
Day 2: _____ mA to _____ mA, notes: _____
Day 3: _____ mA to _____ mA, notes: _____
Day 4: _____ mA to _____ mA, notes: _____
Day 5: _____ mA to _____ mA, notes: _____

5. Stimulate RC (default settings: 10 s between points, 4 reps each, 15 sweeps)
*Note: this takes 10 minutes to complete – warn the participant
6. 1.3x threshold:

Day 1 = _____ mA, Day 2 = _____ mA, Day 3 = _____ mA, Day 4 = _____ mA, Day 5 = _____ mA

tSCS rate-dependent depression:

1. Change name of file to "SubjectID_DayX_tSCSRDD_R1", reset counter to 1
2. Set min and max amplitudes to 1.3x threshold
3. Stimulate **5** pulses with the time between pulses equal to 10 s (0.1 Hz)

Day 1 notes: _____
Day 2 notes: _____
Day 3 notes: _____
Day 4 notes: _____
Day 5 notes: _____

4. Stimulate **5** pulses with the time between pulses equal to 1 s (1 Hz)
Day 1 notes: _____
Day 2 notes: _____
Day 3 notes: _____
Day 4 notes: _____
Day 5 notes: _____

5. **Disable** stimulator

H-reflex threshold:

1. Strap leg to put pressure on electrodes
2. Change name of file to "SubjectID_DayX_Hthresh_R1", set counter to 1
3. Make sure GUI in H-reflex mode
4. Calibrate stimulator
5. **Enable** stimulator
6. Set stimulation amplitude to 5 mA, stimulate single pulse
7. Increase in 1-5 mA increments until have H-reflex in 1 of 3 stimulations
8. Note down H-reflex threshold:
Day 1: occurred at _____ mA in _____ muscle
Day 2: occurred at _____ mA in _____ muscle
Day 3: occurred at _____ mA in _____ muscle
Day 4: occurred at _____ mA in _____ muscle
Day 5: occurred at _____ mA in _____ muscle

M-max on peripheral nerve:

1. Change name of file to "SubjectID_DayX_Mmax_R1", reset counter to 1
2. Set stimulation amplitude to 5 mA above H-reflex threshold
3. Stimulate single pulse, observe motor response
4. Stimulate at higher amplitudes until motor response no longer increasing
 - a. Note: Pk-pk amp in *EMGpk* variable
5. Note down M-max:
Day 1: occurred at _____ mA in _____ muscle
Day 2: occurred at _____ mA in _____ muscle
Day 3: occurred at _____ mA in _____ muscle
Day 4: occurred at _____ mA in _____ muscle
Day 5: occurred at _____ mA in _____ muscle
6. **Disable** stimulator

Peripheral recruitment curve:

1. Calibrate stimulator
2. **Enable** stimulator
3. Change name of file to "SubjectID_DayX_PeriphRC_R1", reset counter to 1
4. Set limits to below H-reflex threshold and above M-max
 - a. Amplitude range:
Day 1: _____ mA to _____ mA, notes: _____
Day 2: _____ mA to _____ mA, notes: _____
Day 3: _____ mA to _____ mA, notes: _____
Day 4: _____ mA to _____ mA, notes: _____
Day 5: _____ mA to _____ mA, notes: _____

5. Stimulate RC (default settings: 10 s between points, 4 reps each, 15 sweeps)

*Note: this takes 10 minutes to complete – warn the participant

6. 1.3x threshold:

Day 1 = _____mA, Day 2 = _____mA, Day 3 = _____mA, Day 4 = _____mA, Day 5 = _____mA

Peripheral rate-dependent depression:

1. Change name of file to “SubjectID_periphRDD_DayX_R1”, reset counter to 1

2. Set min and max amplitudes to 1.3x threshold

3. Stimulate 20 pulses with the time between pulses equal to 10 s (0.1 Hz)

Day 1 notes: _____

Day 2 notes: _____

Day 3 notes: _____

Day 4 notes: _____

Day 5 notes: _____

4. Stimulate 20 pulses with the time between pulses equal to 1 s (1 Hz)

Day 1 notes: _____

Day 2 notes: _____

Day 3 notes: _____

Day 4 notes: _____

Day 5 notes: _____

5. **Disable** stimulator

6. Close reflex GUI

tSCS neuromodulation:

1. Ask participant if they need a break or to use the washroom

2. Set stimulator pulse width to 40 us; output to biphasic

3. Change control of output to the dial

4. Connect bilateral stimulation lead wires

5. Open neuromod GUI (*tSCSguiControlStimv6.m*)

6. **Enable** stimulator

7. Set duration to 15 minutes (900 s), start stimulation, with low amplitude set on the dial

8. Slowly increase stimulation as they get used to the feeling and contractions

9. Set amplitude to

Day 1: _____ mA (engagement of back muscles)

Day 2: _____ mA (engagement of back muscles)

Day 3: _____ mA (engagement of back muscles)

Day 4: _____ mA (engagement of back muscles)

Day 5: _____ mA (engagement of back muscles)

10. Check skin under stimulation electrodes

11. Begin second stimulation (15 minutes (900 s))

Day 1: _____ mA (engagement of back muscles)
Day 2: _____ mA (engagement of back muscles)
Day 3: _____ mA (engagement of back muscles)
Day 4: _____ mA (engagement of back muscles)
Day 5: _____ mA (engagement of back muscles)

12. **Disable** stimulator

13. Disconnect bilateral tSCS lead

REPEAT REFLEXES – Make new folder

Record Impedances:

1. Run reflex GUI (*StimHreflexTMSiv15.m*)
2. Change name of file to “SubjectID_DayX_Impedacnes_R2”, reset counter to 1
Day 1: Day 2: Day 3: Day 4: Day 5:

tSCS threshold:

1. Make sure stimulator PW is 1000 us, set to control mode
2. Place foam behind participant’s back
3. Change name of file to “SubjectID_DayX_tSCSthresh_R2”, reset counter to 1
4. Make sure in PRM-reflexes mode
5. Calibrate stimulator
6. **Enable** stimulator
7. Set stimulation amplitude to 10 mA
8. Stimulate single pulses
9. Increase in 5 mA increments until have PRM-reflex in 1 of 3 stimulations

10. Note down tSCS threshold:

Day 1: occurred at _____ mA in _____ muscle
Day 2: occurred at _____ mA in _____ muscle
Day 3: occurred at _____ mA in _____ muscle
Day 4: occurred at _____ mA in _____ muscle
Day 5: occurred at _____ mA in _____ muscle

tSCS PRM max:

1. Change name of file to “SubjectID_DayX_tSCSmax_R2”, reset counter to 1
2. Stimulate at 10 mA above threshold and observe PRM response
3. Increase by 5-10 mA until have similar amplitude in response as M-max
4. Note down tSCS max:

Day 1: occurred at _____ mA in _____ muscle. Max defined by: _____
Day 2: occurred at _____ mA in _____ muscle. Max defined by: _____
Day 3: occurred at _____ mA in _____ muscle. Max defined by: _____
Day 4: occurred at _____ mA in _____ muscle. Max defined by: _____
Day 5: occurred at _____ mA in _____ muscle. Max defined by: _____

5. **Disable** stimulator

tSCS recruitment curve:

1. Calibrate stimulator
2. **Enable** stimulator
3. Change name of file to "SubjectID_DayX_tSCSRC_R2", reset counter to 1
4. Set limits to below threshold and above max

a. Amplitude range:

Day 1: _____ mA to _____ mA, notes: _____
Day 2: _____ mA to _____ mA, notes: _____
Day 3: _____ mA to _____ mA, notes: _____
Day 4: _____ mA to _____ mA, notes: _____
Day 5: _____ mA to _____ mA, notes: _____

5. Stimulate RC (default settings: 10 s between points, 4 reps each, 15 sweeps)

*Note: this takes 10 minutes to complete – warn the participant

6. 1.3x threshold:

Day 1 = _____ mA, Day 2 = _____ mA, Day 3 = _____ mA, Day 4 = _____ mA, Day 5 = _____ mA

tSCS rate-dependent depression:

1. Change name of file to "SubjectID_DayX_tSCSRDD_R2", reset counter to 1
2. Set min and max amplitudes to 1.3x threshold
3. Stimulate **5** pulses with the time between pulses equal to 10 s (0.1 Hz)

Day 1 notes: _____
Day 2 notes: _____
Day 3 notes: _____
Day 4 notes: _____
Day 5 notes: _____

4. Stimulate **5** pulses with the time between pulses equal to 1 s (1 Hz)

Day 1 notes: _____
Day 2 notes: _____
Day 3 notes: _____
Day 4 notes: _____
Day 5 notes: _____

5. **Disable** stimulator

H-reflex threshold:

1. Change electrodes to tibial nerve electrodes, put strap on the leg
2. Change name of file to "SubjectID_DayX_Hthresh_R2", set counter to 1
3. Make sure GUI in H-reflex mode
4. Calibrate stimulator
5. **Enable** stimulator
6. Set stimulation amplitude to 5 mA, stimulate single pulse
7. Increase in 1-5 mA increments until have H-reflex in 1 of 3 stimulations
8. Note down H-reflex threshold:
Day 1: occurred at _____ mA in _____ muscle
Day 2: occurred at _____ mA in _____ muscle
Day 3: occurred at _____ mA in _____ muscle
Day 4: occurred at _____ mA in _____ muscle
Day 5: occurred at _____ mA in _____ muscle

M-max on peripheral nerve:

1. Change name of file to "SubjectID_DayX_Mmax_R2", reset counter to 1
2. Set stimulation amplitude to 5 mA above H-reflex threshold
3. Stimulate single pulse, observe motor response
4. Stimulate at higher amplitudes until motor response no longer increasing
 - a. Note: Pk-pk amp in *EMGpk* variable
5. Note down M-max:
Day 1: occurred at _____ mA in _____ muscle
Day 2: occurred at _____ mA in _____ muscle
Day 3: occurred at _____ mA in _____ muscle
Day 4: occurred at _____ mA in _____ muscle
Day 5: occurred at _____ mA in _____ muscle
6. **Disable** stimulator

Peripheral recruitment curve:

1. Calibrate stimulator
2. **Enable** stimulator
3. Change name of file to "SubjectID_DayX_PeriphRC_R2", reset counter to 1
4. Set limits to below H-reflex threshold and above M-max
 - a. Amplitude range:
Day 1: _____ mA to _____ mA, notes: _____
Day 2: _____ mA to _____ mA, notes: _____
Day 3: _____ mA to _____ mA, notes: _____
Day 4: _____ mA to _____ mA, notes: _____
Day 5: _____ mA to _____ mA, notes: _____

5. Stimulate RC (default settings: 10 s between points, 4 reps each, 15 sweeps)
*Note: this takes 10 minutes to complete – warn the participant
6. 1.3x threshold:

Day 1 = ____mA, Day 2 = ____mA, Day 3 = ____mA, Day 4 = ____mA, Day 5 = ____mA

Peripheral rate-dependent depression:

1. Change name of file to "SubjectID_periphRDD_DayX_R2", reset counter to 1
2. Set min and max amplitudes to 1.3x threshold
3. Stimulate 20 pulses with the time between pulses equal to 10 s (0.1 Hz)
Day 1 notes: _____
Day 2 notes: _____
Day 3 notes: _____
Day 4 notes: _____
Day 5 notes: _____
4. Stimulate 20 pulses with the time between pulses equal to 1 s (1 Hz)
Day 1 notes: _____
Day 2 notes: _____
Day 3 notes: _____
Day 4 notes: _____
Day 5 notes: _____
5. **Disable** stimulator
6. Close reflex GUI

Notes:

Statistical Analysis Plan

We tested for normality using the Shapiro–Wilk test and assessed the homogeneity of variance using Levene's test. A p-value < 0.05 was considered significant.

Grouped threshold data contain the mean threshold across all channels of the HD-EMG grid. We performed a linear correlation between the PRM reflex threshold for each electrode on the HD-EMG grid with its impedance value. We expressed reflex thresholds in units of charge (μC), obtained by multiplying the stimulation amplitude (in mA) by the pulse width (1 ms). To compare the PRM reflex thresholds over 5 days, we performed a one-way analysis of variance (ANOVA) with Bonferroni post-hoc tests.

We created recruitment curves for the PRM reflexes, M-waves, and F-waves by plotting the mean peak-to-peak amplitude of the response from each electrode on the HD-EMG grid as a function of stimulation amplitude. The slope of the recruitment curve corresponded to the slope of the line between the inflection points across the steepest part of the curve.

We determined the change in PPT over time by subtracting the PPT at each location on Day 1 from Day 5. We normalized the PPT at each location to the maximum PPT value recorded for each participant. We expressed the change in PPT on a scale between -1 and 1, where -1 indicated a maximal decrease in PPT, 1 indicated a maximal increase in PPT, and 0 indicated no change in PPT. We also compared the average PPT across all tested locations on each limb between day 1 and day 5 using a paired t-test.

We used repeated measures ANOVA to compare the mean VAS score from all participants across the 5 days. A decrease in the VAS score by 50% and at least 1 point is considered clinically meaningful. We summated the responses from each subsection of the MPQ to obtain a total score. A clinically meaningful decrease in MPQ score is a 5-point decrease.

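### The phantom limb pain hypothesis refers to five days of tSCS, but the last VAS and McGill scores are taken before the fifth session, so they support a claim about four sessions

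*Combined protocol and SAP*

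**What the plan says.** The Objectives describe one tSCS session on each of five days and state the hypothesis: "We hypothesized that, after 5 days of tSCS, spinal reflex hyperexcitability and PLP would decrease".

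The Design section fixes when pain is measured. For the VAS: "At the beginning of each day, the participant rated their PLP over the last 24 hours using the VAS". For the McGill Pain Questionnaire (MPQ) and the pain pressure threshold (PPT): "At the beginning of the first and fifth days, the participant completed the McGill Pain Questionnaire, and we performed the pain pressure threshold test". It also gives the order of the rest of the visit: "Every day, we performed the M-wave and PRM reflex measures, followed by high-frequency tSCS for 30 minutes".

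The step-by-step worksheet agrees. Its Pain Assessments block ("Give participant MPQ, GQPLA Day 1: Day 5", then one VAS entry per day and the algometer table) stands ahead of participant preparation and the tSCS neuromodulation block. The block that follows stimulation repeats impedance and reflex recordings. It contains no VAS, MPQ or algometer step, and no follow-up visit is described.

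The Statistical Analysis Plan (SAP) compares mean VAS over the five days by repeated measures ANOVA, compares PPT on Day 1 and Day 5 by paired t-test, and sets thresholds for a clinically meaningful fall in VAS and MPQ.

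**The concern.** A hypothesis about five days of stimulation needs at least one pain measurement taken after the fifth session, and the schedule contains none. A reader who meets a conclusion worded for five days of tSCS would assume that all five sessions came before the outcome.

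The documents describe no sham or control group, so the within-person change is the only evidence on PLP that the study produces. The amount of stimulation behind that change is therefore part of what it means. The SAP's thresholds for a clinically meaningful change in VAS and MPQ are likewise applied to scores that follow at most four sessions.

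**Working it through.** The documents give no figure for exposure at the last assessment, so there is nothing to reproduce. The check is a count from the schedule.

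**Inputs**
- Sessions: one per day for five days (Objectives), which agrees with the five sessions in one week stated under Design.
- Session length: 30 minutes (Design: "We delivered bilateral tSCS for neuromodulation continuously for 30 minutes, with a break at 15 minutes to inspect the stimulation site"). The worksheet agrees, with two runs of 15 minutes: 2 × 15 = 30.
- Order within a day: pain measures first, stimulation later (Design and worksheet).
- Pain measures after stimulation: none (worksheet, repeat-reflexes block).

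**Sessions completed before the assessment on Day k:** k − 1.

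| Day | Sessions before assessment | VAS | MPQ and PPT |
|---|---|---|---|
| 1 | 0 | yes | yes |
| 2 | 1 | yes | no |
| 3 | 2 | yes | no |
| 4 | 3 | yes | no |
| 5 | 4 | yes | yes |

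**Exposure at the last pain measure**
- Sessions: 4 of 5 = 80%.
- Minutes: 4 × 30 = 120 of 5 × 30 = 150, and 120 / 150 = 80%.
- Sessions that contribute to no pain outcome: 5 − 4 = 1, the fifth.

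**Recall.** The VAS looks back 24 hours. Clock times are not given, so part of the Day 5 window may fall before session 4. The MPQ is introduced this way: "Participants completed the short-form McGill Pain Questionnaire to describe their pain prior to participation in the study as well as throughout the week". That does not settle whether the Day 5 form rates that day or the week. Neither point can raise the count, so four sessions is the most that either self-report can reflect.

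**Reflexes (secondary).** The hypothesis also covers reflex excitability. The worksheet records reflexes before stimulation (R1, after 0 to 4 sessions) and again afterwards (R2, after 1 to 5 sessions). The SAP does not name the run used in the PRM threshold ANOVA. The Design section describes only measures taken before tSCS, which points to R1. If R1 is used, that comparison also ends after four sessions.

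**The case against.** The strongest reply is that this is a gap of one session in one sentence, and that the timing is sensible. Measuring before stimulation on each day compares like with like and keeps the immediate effects of that day's session out of the score. A 24-hour VAS completed straight after session 5 would mostly rate the time before it. This stands: the schedule is defensible, and the planned tests are not made invalid by it. It does not make the hypothesis sentence accurate.

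Three stronger readings are tempting, and the documents do not support them.

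- A reader might infer that the PPT analysis also contradicts the hypothesis. It does not. The hypothesis names reflex hyperexcitability and PLP. PPT is pressure sensitivity tested on both legs and, on the worksheet, the arms, and no five-session claim is attached to it.
- A reader might infer that the SAP itself misstates exposure. It does not. It refers to comparisons over the five days and between Day 1 and Day 5, which is correct as calendar wording. The mismatch lies in the Objectives and in any conclusion that adopts their wording.
- A reader might infer from the MPQ description that its Day 5 score reflects clearly fewer than four sessions. The questionnaire form is not reproduced, and the phrase may simply describe the two administrations. No lower figure can be supported.

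**Conclusion.** The point holds for PLP as measured by VAS and MPQ. The design as written does not observe pain after the fifth session, so it supports a statement about four sessions (120 of 150 minutes) and not about five. This rests only on the order of events, on which the Design section and the worksheet agree, and on one session being given per day as planned.

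A reader might go further and infer that the pain results are biased, or that an effect is understated. The documents do not allow that. They do not say how change builds up or wears off between sessions, so neither the size nor the direction of any difference from a five-session result can be computed. The 80% is a share of stimulation delivered, not of effect.

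The reflex part is conditional on R1 being the run analysed, which the documents suggest but do not state. The correction is cheap and changes what may be concluded, so it should be made.

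**What to change.** 1. Restate the PLP hypothesis, and any conclusion drawn from VAS or MPQ, as within-person change from before session 1 to before session 5, that is, after four sessions. This is wording only; the price is a narrower claim.
2. If data can still be collected, add one VAS and one MPQ at least 24 hours after session 5, with the same recall wording as before, as the five-session pain outcome. The 24 hours ensure that the VAS window lies wholly after that session. The cost is one short contact per participant. The narrative is in the past tense, so this may no longer be possible; in that case item 1 is sufficient.
3. When PPT is reported, describe its Day 5 minus Day 1 change as after four sessions. The analysis needs no change.
4. State in the SAP which reflex run enters the PRM threshold ANOVA. If it is R1, describe that result as after four sessions too. This takes one sentence.

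### The worksheet puts the Day 1 and Day 5 pressure-threshold columns side by side, so an unmasked operator would probably see each Day 1 value while taking the Day 5 reading

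*Combined protocol and SAP*

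**What the plan says.** **Layout.** The worksheet (Pain Assessments, step 2) logs the pain rating on one line for all five days: "Give participant VAS Day 1: Day 2: Day 3: Day 4: Day 5". The algometer table in step 3 lists sites down the page, with adjacent columns for Day 1 and Day 5 in lbf. Under tSCS threshold, the instruction "Note down tSCS threshold" is followed by five stacked lines of the form "Day 2: occurred at _____ mA in _____ muscle". The H-reflex threshold, M-max and PRM maximum are laid out in the same way.

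**How PPT is taken.** The Design section says: "The participant reported when the pressure became painful, at which point we removed the algometer and recorded the pressure magnitude". On timing it says: "At the beginning of the first and fifth days, the participant completed the McGill Pain Questionnaire, and we performed the pain pressure threshold test". It describes no rate of application, masked read-out or repeat reading.

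**How the bedside reflex threshold is taken.** The worksheet rule is "Increase in 5 mA increments until have PRM-reflex in 1 of 3 stimulations", with no amplitude criterion for what counts as a reflex.

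**How the readings are analysed.** The SAP averages PPT over the tested locations on each limb and compares Day 1 with Day 5 by a paired t-test. It also forms a normalised change per site from the same readings. For reflex thresholds it says: "Grouped threshold data contain the mean threshold across all channels of the HD-EMG grid".

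**Design.** Every participant receives tSCS. No control, sham, randomisation, blinded assessor or withholding of earlier entries is described.

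**The concern.** PPT depends on two people. The participant says when pressure becomes painful, but the operator sets how fast the force rises, reacts to the report and reads off the number. An operator with the Day 1 value in the next column has an anchor for each of these acts.

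If the anchor moves the Day 5 readings the same way at each site, averaging over sites gives no protection. Averaging shrinks independent error and leaves a common shift whole. In a controlled comparison with blinded readings, such a shift would tend to fall on both arms and cancel. Here it would be read as change over the week of stimulation.

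A secondary worry is the reflex search. It is called live, by eye, with earlier days' amplitudes stacked under the same heading. That call feeds the recruitment-curve range and the 1.3x-threshold amplitude used for rate-dependent depression.

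**Working it through.** The plan gives no sample size, SD or effect size for PPT, so there is no figure of its own to reproduce. The check has three parts.

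**1. Does a common shift average out?** The worksheet lists 11 residual-limb sites: the stump end, four at 5 cm, four at 10 cm, mid-quad and mid-hamstring. Write the Day 5 minus Day 1 difference at site j as d_j = t_j + b + e_j. Here t_j is the true change, b is the operator shift and e_j is independent error with variance s². The limb mean is mean(t) + b + mean(e). The variance of mean(e) is s²/11, but b enters at full size.

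**2. What could b do to the paired t-test?** Inputs from the documents: a paired t-test at the 0.05 level. Assumed: two-sided testing (not stated), analysis in raw lbf, no true change, the shift b, the SD of participants' limb-mean change, and n.

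The noncentrality is b / (SD / √n) on n − 1 degrees of freedom. The false-positive rate is the probability that a noncentral t exceeds the two-sided critical value in either direction.

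Worked case with b = 0.3, SD = 0.8 and n = 10: noncentrality = 0.3 / (0.8 / √10) = 1.186; critical value 2.262 on 9 df; false-positive rate 18.6%.

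| Shift (lbf) | SD (lbf) | n = 6 | n = 10 | n = 20 |
|---|---|---|---|---|
| 0.3 | 0.8 | 11.7% | 18.6% | 35.7% |
| 0.3 | 2 | 6.1% | 7.1% | 9.8% |
| 0.3 | 4 | 5.3% | 5.5% | 6.2% |
| 0.5 | 0.8 | 23.9% | 42.3% | 75.5% |
| 0.5 | 2 | 8.0% | 10.9% | 18.6% |
| 0.5 | 4 | 5.7% | 6.5% | 8.3% |

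With no shift, every cell would be 5%. The table shows what a given shift would do. It is not evidence that the layout causes one.

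**3. Where does the bedside reflex threshold go?** Following it through the documents:

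- The worksheet records one amplitude in one muscle.
- A call one step early or late moves that value by 5 mA, which is 5 mA × 1 ms = 5 µC in the SAP's unit. It moves the 1.3x-threshold amplitude by 1.3 × 5 = 6.5 mA.
- The threshold also helps to set the recruitment-curve limits.
- The analysed threshold is a mean over HD-EMG grid channels. The SAP does not say how each channel's threshold is found, so the step from the handwritten entry to the ANOVA is not established.

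**The case against.** The strongest case on the other side has five parts.

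- **Visibility is inferred.** The documents contain a blank template. They do not say that one copy is carried through the week or that earlier entries are in view. This stands, and it is why the point says "probably". For PPT there is also only one earlier reading to see, that of Day 1.
- **No direction is hypothesised for PPT.** The stated hypotheses concern reflex excitability and phantom limb pain. The participant's report also ends each trial. Both points stand. A shift of one sign across sites is a plausible risk and has not been shown.
- **The size rests on assumption.** SD, shift and n are all outside the documents, and at an SD of 4 lbf the inflation nearly vanishes. This stands.
- **The reflex search has some protection.** It restarts at 10 mA in fixed 5 mA steps each session, and recruitment amplitudes are delivered in random order. This limits anchoring but does not remove it, since what counts as a reflex is still judged by eye.
- **The larger weakness is the uncontrolled, unblinded design.** An operator can remember Day 1 and knows which day it is. This stands: separate sheets give partial protection only.

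A reader might also infer that the VAS is contaminated. The documents do not support that: "the participant rated their PLP over the last 24 hours using the VAS", so the score is the participant's own. Nothing shows that participants see earlier scores or lack a fresh sheet. Nor do the documents support a view that recruitment limits are borrowed from other days. The worksheet finds a threshold and maximum in each session and sets the limits from those.

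**Conclusion.** The point holds in a narrow form and is a minor one. For PPT, three things together make anchoring a real and avoidable risk: adjacent Day 1 and Day 5 columns, an operator who controls the pressure with no masking described, and a paired test with no control arm. It rests on the assumption that the same form is used on both days.

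The size cannot be fixed from the documents. For a 0.3 lbf shift and 6 to 20 participants, the illustrative false-positive rate runs from about 12–36% at an SD of 0.8 lbf, through about 6–10% at 2 lbf, to about 5–6% at 4 lbf.

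For reflex thresholds, the layout could anchor the bedside call and so the settings derived from it. A reader might go further and conclude that the five-day threshold ANOVA is biased. The documents do not support that, because the analysed value is a channel mean with no stated link to the handwritten one.

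**What to change.** **For any further data collection:** use a separate sheet for each day for the PPT readings and the bedside reflex searches, and keep earlier sheets out of the operator's sight during the session.

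**For data already collected** (the document describes the study in the past tense): state whether Day 1 PPT values were visible to the operator on Day 5, and report this as a limitation of the PPT result. A sentence in the SAP on how each HD-EMG channel's threshold was derived would settle whether the bedside call can reach the analysis.

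**Cost:** re-laying out the worksheet and a few sentences of reporting. Staff lose the convenience of glancing at earlier values. The operator may still remember Day 1, so the protection is partial and does not replace a control arm or blinded assessment.
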